4.1. Risk- benefit assessment and management

Our study's main benefit is that it may reduce psychological distress and improve functioning. ESTAIR is an evidence-based intervention. Our cultural adaptations have relied on evidence-based literature and fieldwork. Based on these facts, we assume that the ESTAIR intervention can reduce psychological distress symptoms.

The study entails only minimal risks for participants. The ESTAIR manual corresponds to the guidelines for treating PTSD. Yet, there is a risk that parts of the intervention will destabilize the participants during therapy. Evidence from face-to-face treatments suggests that between 5% and 10% of all patients experience a deterioration of their symptoms during treatment. However, this destabilization will be temporary, and overall, on the longer term, the program is considered beneficial, as evidence shows that culturally adapted trauma-focused interventions are effective [49] . Furthermore, the manual's first module, emotion regulation skills, aims to teach participants how to manage difficult emotions and stress. This will help them during the course of the intervention.

As in any clinical study, severe adverse events such as misuse of alcohol or drugs, self-harm, or suicidal ideation or attempts can occur during participation in the trial. The therapists will receive regular supervision from senior experts. They are trained for situations of crisis, such as severe emotional distress, dissociation, a temporal increase of suicidal thoughts, or other negative reactions to the treatment. Please refer to Section 4.2 for the protocol for adverse events and crisis situations.

Participants will receive therapy at no cost and will be compensated for all assessment and feedback interviews. Aside from attending the therapeutic program and assessments, no other commitments will be asked from them.

4.2. Adverse Events

Procedures to handle Adverse Event AE

An Adverse Event (AE) is any untoward medical occurrence in a patient or a clinical investigation subject that does not necessarily have a causal relationship with the trial procedure. An AE can therefore be any unfavorable or unintended finding, symptom, or disease temporarily associated with a trial procedure, whether or not related to it.

A Serious Adverse Event (SAE) is any untoward medical occurrence that results in death, is life-threatening, or requires in-patient hospitalization or prolongation of existing hospitalization.

Although likely uncommon, all adverse events (AEs) and serious adverse events (SAEs) reported by the participant or identified by the therapists at any time will be recorded for immediate action and resolution where required to ensure participant safety.

All SAEs are documented and reported immediately (within a maximum of 24 hours) to the UniL Supervisor, [name], and the AUC Advisor, [name]. The team will have a debriefing meeting, and the concerned ethics committees will be informed, within 15 days.

As a part of the study procedures, all participants who will be included in the study will receive a list of available mental health services. Please see Appendix 6. These services include emergency services and other out-patient services, if necessary. Out-patient clinics are provided if participants require psychiatric medication consultations during the study. All services are trusted and offer standard care. During the introductory session, therapists will remind participants of this and direct them to emergency services. They will also inform participants that if they notice any changes in suicidal thoughts or psychotic symptoms, they should report them. Intermediate assessments will include an oral check for suicidality. We will provide participants with the therapists' work phone number, emphasizing that they should only use it in emergencies. They will also be informed that, due to work schedules, therapists may take up to 24 hours to respond to their calls. Should a therapist receive a phone call from participant they will assess the risk:

If the risk is not imminent, the therapist will provide information on where to seek care and remind participants of key emotion regulation techniques to tolerate distress until the next group meeting. See the services list for referral information, which comprises a list of mental health services including psychiatric, psychological, and alternative sources of help (e.g., specialized phone hotlines).

If the risk is imminent, the therapist will suggest the following: If possible, the participant should find someone trusted to stay with them or, in cases of emergencies, accompany them immediately to their respective services. If the participant cannot contact a trusted person, the therapist can ask him or her to provide their phone number. The therapist can then contact the trusted person and describe the situation. The therapist will call the participant again after calling the trusted person to update them. If no trusted person is available, the therapist will direct participants to seek emergency services on their own or contact relevant hotlines, such as suicide hotlines. The therapist will call again to check on the participant.

Therapists are trained to handle such situations, and all similar situations will be brought to group or peer supervision meetings.

In the case when one of the therapeutic teams wants to discuss or receive feedback from the rest of the team regarding the state of a specific client, such information will be discussed in team supervision and peer supervision meetings, which include both psychologists and psychiatrists for multi-disciplinary clinical perspectives. The confidentiality of patients will be respected. In the case of pre-mature termination due to risk or AE, the UniL Supervisor, [name], and the AUC Advisor, [name], will be informed.

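### Substance misuse, self-harm, dissociation, severe distress and hospitalisation have no scheduled enquiry in the available text, so the pilot's harm record will lean towards under-reporting

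*Combined protocol and SAP*

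**What the plan says.** Section 4.1 says that "severe adverse events such as misuse of alcohol or drugs, self-harm, or suicidal ideation or attempts can occur during participation in the trial". It adds that therapists are trained for crises such as "severe emotional distress, dissociation, a temporal increase of suicidal thoughts, or other negative reactions to the treatment", and refers to section 4.2 for the procedure. It also cites evidence that "between 5% and 10% of all patients experience a deterioration of their symptoms during treatment", and it opens its account of risk with the statement "The study entails only minimal risks for participants".

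Section 4.2 defines a serious event as one that causes death, threatens life, or leads to or prolongs a hospital stay. On capture it says that "all adverse events (AEs) and serious adverse events (SAEs) reported by the participant or identified by the therapists at any time will be recorded". One enquiry is scheduled: "Intermediate assessments will include an oral check for suicidality". Participants are also told that "if they notice any changes in suicidal thoughts or psychotic symptoms, they should report them", and they are given a therapist telephone number for emergencies only.

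Three other parts of the protocol bear on the point:
- Section 3.8 has every candidate asked at screening about suicide risk, psychosis and severe alcohol or drug abuse. After each module, participants complete all outcome measures.
- Section 3.10 describes those measures as covering CPTSD symptoms, depression, anxiety, somatic symptoms and well-being.
- Section 3.12 provides for follow-up of people who drop out, with feedback interviews where possible.

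**The concern.** The harms in section 4.1 and the enquiries in section 4.2 do not match. Substance misuse is asked about at entry and named as a possible harm during the trial, but no later question about it is described. The same holds for self-harm as an act, for dissociation, and for emergency or hospital visits, although hospitalisation is part of the definition of a serious event.

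Two things are at stake. First, when nobody is asked, an absence of recorded events cannot be told apart from an absence of questions, and the error runs towards apparent safety. Section 11 presents the pilot as the step before a fully powered randomised trial, so its harm record should be interpretable. Second, section 4.2 records events so that they can be acted on at once, and an event that nobody mentions cannot be acted on. Spontaneous disclosure may also be difficult here: Modules 1 to 3 and the participant feedback are in group format (section 3.8), and the protocol itself points to stigma (sections 1.5 and 3.8).

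**Working it through.** **Harms against planned enquiry, from the available text**

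| Harm | Where named | Scheduled enquiry after baseline |
|---|---|---|
| Suicidality | 4.1 | Oral check at intermediate assessments; the post-assessment is not mentioned |
| Symptom deterioration | 4.1 | Outcome questionnaires after each module and at the end (3.8, 3.10) |
| Severe emotional distress | 4.1 | Partly, through the depression and anxiety scores |
| Alcohol or drug misuse | 4.1 | None described |
| Self-harm as an act | 4.1 | None described beyond the suicidality check |
| Dissociation | 4.1 | None described |
| Hospitalisation | 4.2 | None described |

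The questionnaire scores are not linked to adverse event recording, and section 3.11 gives no threshold for deterioration.

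**Size**

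The plan states no event rate, safety sample size or safety precision, so there is no figure of its own to reproduce.

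Inputs:
- n = 20 (section 3.6), which agrees with four groups of five (4 × 5 = 20, section 3.8).
- p, the true proportion of participants with an event. Values of 5% and 10% are used for illustration. They are the ends of the deterioration range in section 4.1 and are not stated there for the harms at issue.
- s, the share of affected participants whose event is recorded. Values of 0.75, 0.5 and 0.25 are assumptions, since the documents give none.

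Participants are treated as independent.

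*Upper bound after 0 of 20.* The one-sided 95% limit on the recorded rate is 1 − 0.05^(1/20) = 13.9%. Because the recorded rate is p × s, the limit on p is 13.9% / s.

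*Chance of recording no event.* This is (1 − p × s)^20. For example, with p = 10% and s = 0.5 it is 0.95^20 = 35.8%.

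| Capture share s | Upper bound on p after 0 of 20 | Chance of no record, p = 10% | Chance of no record, p = 5% |
|---|---|---|---|
| 1 (full) | 13.9% | 12.2% | 35.8% |
| 0.75 | 18.5% | 21.0% | 46.6% |
| 0.5 | 27.8% | 35.8% | 60.3% |
| 0.25 | 55.6% | 60.3% | 77.8% |

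The first row is what the sample size alone imposes. The lower rows show what incomplete capture adds. At p = 10%, halving capture raises the chance of an empty record by 35.8 − 12.2 = 23.6 percentage points.

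The sample-size limit is wider still for Module 4, which 5 to 10 participants receive (section 3.8). With full capture, no events gives 1 − 0.05^(1/10) = 25.9% for ten participants and 1 − 0.05^(1/5) = 45.1% for five.

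**The case against.** The other side has a strong case on several counts.

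- A reader might infer that the trial will use a low event count to justify "The study entails only minimal risks for participants". The documents do not support that. The statement is made in advance in the ethics section and is followed at once by an acknowledgement that therapy may destabilise participants. The analysis plan contains no adverse event summary, and section 4.2 records events for action, not to estimate rates. Such a use is possible later but is not planned.
- A reader might infer that suicidality is the only harm measured in everyone. That is too broad. Deterioration, the only harm to which section 4.1 attaches a rate, is covered by questionnaires after each module, and section 3.11 sets a change status for each participant.
- A reader might infer that participants are never asked about the remaining harms. That cannot be shown. The fidelity form (Appendix 4), the questionnaires (Appendix 7) and the interview guides (Appendix 8) were not available and may hold relevant items.
- Twenty participants give weak evidence on harms however events are found. Even with full capture, 0 of 20 does not exclude the 5% to 10% range, and a checklist does not change that.
- Group format does not close every route. Module 4 is individual, section 3.8 does not say that the assessments are held in groups, and there are the telephone line and the drop-out contact.

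All of this stands and limits the point. It does not remove the mismatch. The alternative routes still depend on the participant raising the matter or, for drop-outs, serve to learn why they left. Imprecision from a small sample is also a different problem from a bias towards under-reporting, and the second can be reduced cheaply.

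**Conclusion.** The point holds for alcohol or drug misuse, self-harm, dissociation, severe distress (which the questionnaires cover in part) and hospitalisation. In the available text these are captured only by spontaneous report or therapist observation. It does not extend to symptom deterioration, and it does not show that the trial plans a safety claim from event counts.

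Passive capture biases the harm record towards under-reporting. After 0 of 20, the one-sided 95% upper bound is 13.9% with full capture and 27.8% at half capture, with a range of 18.5% to 55.6% across capture shares of 75% to 25%. Those shares are assumptions, so the figures illustrate the effect and do not estimate it. The conclusion also depends on Appendices 4, 7 and 8 holding no equivalent items. This is an improvement that should be made. It is not a flaw in the pilot's primary aims of feasibility and acceptability.

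**What to change.** First check Appendices 4, 7 and 8. If they already ask about these harms, cite the items in section 4.2 as a capture route and say who is asked and when.

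Otherwise, extend the existing oral check:
- **When:** at each post-module assessment, at the post-assessment, and at the drop-out contact in section 3.12.
- **How:** ask each participant individually, outside the group, a short fixed yes/no list covering substance misuse, self-harm, dissociation or severe distress, and emergency or hospital visits, plus one open question on unwanted events.
- **Record:** enter the answers on one REDCap form and handle positive answers under the procedures already in section 4.2.
- **Report:** give the number of participants with each event and the number asked, with solicited and spontaneous reports shown separately.

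The cost is a few minutes at three assessments in the three-module plan or four in the four-module plan, one form, and a protocol amendment submitted under section 4.4. No new visit or post is needed. Section 3.8 names therapists, co-facilitators and research assistants in different sentences as assessors, and the only training it states for the research assistants is the Citi course. The amendment should therefore say who asks the questions and how that person is prepared for disclosures. The recorded event count will rise, so it should not be compared directly with counts from studies that relied on spontaneous reports.

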Participants will then be asked to fill self-report questionnaires. Please see Section 3.10 for outcome measures. Patients will be given the option to either complete the self-report questionnaires themselves, or, if they prefer to have the therapist read the items to them. If the participant screens positive for CPTSD using the ITQ. They will then be informed that they are eligible and asked to join our study. If they agree to join, we will collect socio-demographic data, i.e., sex, age, religion, marital status, education, occupation, income.

Participants will receive compensation of 700 EGP for this session.

Cultural module-ITI pilot

At the end of this interview, patients who have screened positive for CPTSD will be asked if they are interested in participating in two formulation sessions to pilot the ITI and the cultural and structural module (please see Section 3.5). This question will be asked to participants whether they are interested in joining our therapy program or not. These sessions will be conducted independently of the screening and therapy process. Participants will be informed that their decision will not impact their inclusion in the therapeutic program and will be reminded that they have the right to decline. They will be reminded about their voluntary participation and the possibility of withdrawal at any time. They will be given a separate consent sheet and will also be informed that their time will be compensated. Please see appendix 2 for consent forms.

NH will conduct the ITI (original version and additional items of the cultural and structural module), to assess the feasibility and cultural applicability of the added module. She will be trained along with the UniL team to conduct the clinical interview. ITI formulation sessions will be audio recorded for research purposes. We will record sessions to use them to collect idioms of distress, free-listed symptoms, and cultural norms as a part of the ethnopsychological portion of this study, which will allow us to further adapt the diagnostic module and the therapy in the future. We did not conduct interviews with patients during the formative research phase (only mental health professionals, and family members/close ones of individuals exposed to violence). This was due to the high vulnerability of our population, as it would have been unethical to cause distress through interview questions without providing a treatment option.

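### The therapists' number is reserved for emergencies yet may go unanswered for up to 24 hours, so the therapist-led telephone pathway, though not all access to emergency care, can fail

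*Combined protocol and SAP*

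**What the plan says.** Section 4.2 (Adverse Events) supplies participants with the therapists' work number, "emphasizing that they should only use it in emergencies". The next sentence tells them that "due to work schedules, therapists may take up to 24 hours to respond to their calls". The telephone procedure then opens with a condition: "Should a therapist receive a phone call from participant they will assess the risk".

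For imminent risk, the section sets out an order of steps. The participant first tries to find someone trusted. Next, "If the participant cannot contact a trusted person, the therapist can ask him or her to provide their phone number"; the therapist may then phone that person, explain what is happening, and ring the participant back. Finally, "If no trusted person is available, the therapist will direct participants to seek emergency services on their own or contact relevant hotlines", and the therapist calls again to check.

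At enrolment, Section 3.8 says that "we will collect socio-demographic data, i.e., sex, age, religion, marital status, education, occupation, income". Neither the prescreening nor the screening and consent text mentions a trusted or emergency contact.

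Section 4.2 also contains safeguards that do not depend on the phone: "all participants who will be included in the study will receive a list of available mental health services", and "During the introductory session, therapists will remind participants of this and direct them to emergency services". Intermediate assessments include an oral suicidality check. Section 3.9 separately covers an immediate suicide threat or severe psychotic symptoms, with suspension of therapy, guidance to services and team review of the case.

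**The concern.** The only use allowed for the number is the one that a response time of up to a day serves least well. A participant who follows the instruction may wait a long time, and nothing on the therapist's side starts until contact is made.

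The second-line step has a related weakness. It needs a third party's number, which the supplied text has the therapist obtain only by speaking to the participant in crisis. If the therapist returns a call hours later and nobody picks up, the procedure gives no further step, and the supplied text gives the therapist no other person to try.

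What is at stake is participant safety. The protocol foresees the situation: Section 4.1 names self-harm and suicidal ideation or attempts as events that may arise during the trial. Exclusion of imminent suicide risk at entry (Section 3.6) does not cover risk that emerges during therapy.

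**Working it through.** The plan's one figure here is a stated operating limit (24 hours), so there is nothing to recalculate. The check sets the provisions side by side and follows a call through them.

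1. **Purpose against response time (Section 4.2).** Purpose: "emphasizing that they should only use it in emergencies". Response: up to 24 hours. These stand in consecutive sentences and concern the same number. Warning participants of the delay is honest, but it does not make the two statements compatible.

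2. **What starts the pathway (Section 4.2).** The risk assessment depends on a therapist receiving the call. There are three cases:
   - *Call answered.* All steps are available.
   - *Call missed, call-back answered.* All steps are available, after a delay of up to 24 hours.
   - *Call missed, call-back not answered.* No step is written for this case.

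3. **What the trusted-person step needs.** The participant's own attempt comes first and needs nothing from the therapist. The therapist's attempt comes second, is worded as optional, and needs a number given during the conversation. In the third case above, that conversation does not take place.

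4. **Whether the number could already be held (Section 3.8).** Prescreening shows that the team has the participant's own contact details, since the consent sheet is sent to them. Screening, consent and the socio-demographic list add no third-party contact. That list is not an inventory of everything the team holds. The consent forms (Appendix 2), questionnaires (Appendix 7) and data management plan (Appendix 9) were not supplied. The finding is therefore that no contact field appears in the supplied text, not that none exists.

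5. **Scheduled checks between calls (Sections 3.8 and 4.2).** The oral suicidality check is attached to intermediate assessments: weeks 6 and 12 in the three-module plan, and weeks 6, 12 and 17 in the four-module plan. Final sessions are at weeks 18 and 25. The last stated check therefore precedes the final session by 18 − 12 = 6 weeks in one plan and 25 − 17 = 8 weeks in the other. Sessions continue in those intervals, so contact is not lost, but a change between sessions depends on the participant reporting it.

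6. **Extent.** The arrangement applies to all 20 planned therapy participants. Section 4.1 cites deterioration in 5% to 10% of patients in face-to-face treatment: 0.05 × 20 = 1 to 0.10 × 20 = 2 participants. That is symptom deterioration, not suicidality, and it does not estimate emergency calls. The documents give no basis for such an estimate.

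**The case against.** The strongest reply is that the phone is one route among several. Every included participant holds the services list, is directed to emergency services at the introductory session, and is told of the possible delay, so nobody is led to expect an instant answer. Within the telephone steps, the participant's own contact with a trusted person comes first. The therapist's request for a number is second-line, and a third step and a check-back call follow. Section 3.9 handles an immediate threat without needing a call.

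Most of this stands, and it limits the point. A reader might infer that a participant in crisis has no route to emergency care, or that the whole safety plan fails with the phone. The documents do not support that: the list, the advance direction and Section 3.9 all operate independently of the number.

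A reader might also infer that someone who discloses risk at an oral check and then stops attending falls through entirely. Section 3.9 covers an immediate threat, and Section 3.12 commits the team to follow up those who withdraw, so that case is at least partly covered.

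Nor do the documents show that no trusted contact is ever recorded, because the appendices were not supplied.

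The objection does not remove the conflict between the two sentences on the number, or the missing step for an unanswered call-back.

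**Conclusion.** The point holds for the therapist-led telephone pathway. Followed as written, an emergency-only number can go without a response for up to 24 hours, the therapist's steps wait on contact being made, and an unanswered call-back leads nowhere in the text. Access to emergency care by other routes remains.

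This is an inconsistency in a safety procedure and should be corrected. It does not affect any estimate or test in the statistical analysis plan. Its size is the stated delay of up to 24 hours across the 20 planned participants; its frequency is unknown.

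The conclusion on the trusted contact rests on one assumption: that the unsupplied appendices do not already provide for collecting one. If they do, that part reduces to a missing cross-reference in Section 4.2. The conflict over the number does not depend on this assumption.

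**What to change.** - **Section 4.2, purpose and response time.** Reconcile what participants are told the number is for with the response time stated for it. The clinical leads should decide which statement changes and how.
- **Section 4.2, telephone steps.** Reconcile the imminent-risk steps with both statements, including the case of a call-back that is not answered. The content is for the clinical leads; no response time or crisis rule is proposed here.
- **Section 3.8, enrolment.** Unless an appendix already does this, add an optional trusted-contact field, with consent for that person to be contacted, which participants can decline or update. If an appendix already has one, refer to it in Section 4.2. Prior consent also matters because the therapist may describe the participant's situation to this person, and Section 1.5 reports domestic violence and stigma in this setting.
- **Section 5.2, storage.** Keep the contact secure but within the therapists' reach. Section 5.2 holds the code list in physical form, apart from the data, so storing the contact only there could make it unavailable when needed.

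The cost is a revision of Section 4.2, plus one field and one consent sentence at a visit already planned. The downsides are one more item of identifying data to protect, some participants declining to name anyone, and, in a violence-exposed population, the possibility that a named contact later becomes unsafe and must be updated.
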